## 2. SYNOPSIS

1. Title of study	Managing Congestion in Heart Failure: Pressure- and Volume- based. A mechanistic study in patients with HFpEF (MAGIC-HF)
2. Hypothesis	We hypothesize that remote monitoring (RM) in patients with heart failure (HF) with preserved (HFpEF) ejection fraction using a smart scale to measure extracellular and total amount of water in different segments of the body in parallel to monitoring pulmonary pressure improves the management of congestion in patients with HF. This leads as a result to an improvement of NT-pro-BNP and renal function.
3. Objective of the study	We plan a mechanistic RM-study in patients with HFpEF, who have the indication for RM using CardioMEMS™. Data transmitted from CardioMEMS™ and from the smart scale will be monitored on daily basis in order to understand the mechanism of changes taking place during the study duration (6 months) in both pulmonary pressure and in volume represented as extracellular and total amount of water in the upper and lower extremities as well as in the trunk. This should allow us to reach an euvolemic state in patients with HF, which is often an unmet need.
4. Background	
In patients with heart failure (HF) the absolute number of hospitalizations and the rates of HF readmissions is still high with a significant financial burden associated. As a result, reducing readmission rates has become a priority in many of the developed countries. Currently 25% of patients with HF are readmitted within one month of discharge.
 
Achieving and maintaining an euvolemic status through managing congestion is a key goal in the management of HF. Thus, close observation of, and rapid response to changes of early physiological indicators are essential in achieving or maintaining euvolemia. Clinical signs and symptoms of cardiac decompensation are preceded by an increase in filling pressures and autonomic adaptation. Furthermore, clinical signs and symptoms are neither sensitive nor specific for detecting congestion. We have shown in a previous study in patients with HF and sleep apnea increased amounts of both extracellular and total amounts of water compared to those with HF but without sleep apnea. The increased amount of water was not associated with clinical cardiac decompensation. We called this clinically pre-congestion. An increased amount of water was associated with worse exercise capacity and with an elevated apnea/hypopnea index.
 
As such, new means and technologies to improve monitoring of such parameters and care delivery are urgently required. Novel technologies of telemedicine or RM such as CardioMEMS™ (Abbott Laboratories, Chicago, IL, USA), which is a small sensor placed in the pulmonary artery to monitor the pulmonary pressure, represent a possible solution to the above-mentioned unmet needs in patients with HF.
 
However, the principle that volume equals pressure has been challenged recently. Based on data from CardioMEMS™ and systems enabling estimation of the intravascular volume such as blood volume analysis (BVA-100, Daxor Corporation, New York, NY, USA), the current approach of HF-Therapy using diuretics to decongest these patients appeared not to be always the best decision. The reason is that some of those patients with elevated pulmonary pressure (CardioMEMS™) appeared to be euvolemic or hypovolemic. It was postulated that congestion is a result of changes occurring in both volume and pressure.
 
Additionally, severe congestion is supposed to be associated with inflammation, mechanical stress, and endothelial dysfunction. Thus, identifying surrogate biomarkers for all of these processes in addition to monitoring volume and pressure simultaneously


	
and continuously for 6 months would help to better understand congestion and its management.
 
This is indeed an important concept and a clinically relevant question to characterize patients in different phenotypes as following: elevated/low pressure with hypervolemic, euvolemic or hypovolemic. Managing congestion in patients with HF might be optimally achieved by both monitoring pulmonary pressure and volume status.

5. Number of patients	20 Patients with HFpEF. Dropout 20%. Total number of patients 25 patients.
6. Number of sites	
Four sites.
 
 
- Department of Cardiology and Angiology, University Hospital Magdeburg, Germany.
 
- Department of Cardiology and Angiology, University Hospital Giessen, Germany
 
- Department of Cardiology, Deutsches Herzzentrum der Charité, Berlin, Germany
 
- Department of Cardiology, University Hospital Wuerzburg, Germany
 

7. Length of follow-up	
The planned follow-up duration is 6 months
 
Time from first patient in to last patient out 12 months.

8. Data to be collected	
All patients will get following tests at baseline: Echocardiography (left ventricle ejection fraction (LVEF), E/e', left atrial volume index (LAVI), left atrial strain analysis, left ventricle mass index (LVMI), tricuspid annular plane systolic excursion (TAPSE), right ventricle strain, inferior vena cava IVC), and blood tests: N-terminal pro-b-type natriuretic peptide (NT-proBNP), creatinine, glomerular filtrating rate (GFR), soluble suppression of tumorigenicity (sST2) as a surrogate of intravascular congestion, carbohydrate antigen 125 (CA 125) and bio-adrenomedullin (bio-ADM) as surrogates of tissue congestion (extracellular water). Additionally, ALAT, ASAT, complete blood count, and hsCRP will be documented. Evaluation of extracellular and total amounts of water volume segmentally (arms, legs, trunk) using the smart scale (Body water scale InBody, South Korea) as well as pulmonary pressure (CardioMEMS™) will be done at the same time.
 
We will gather daily data of pulmonary pressure (CardioMEMS™) and water volume using a smart scale. The evaluation of volume will be based on bioelectric impedance analysis (BIA).
 
Following blood tests will be monitored at weeks 2, 6, 12 and at the final visit: NT-proBNP, creatinine and GFR, ALAT, ASAT, hemoglobin, hematocrit, hsCRP, sST2, CA 125, and bio-ADM.
 
Tests and investigations at the final visit: Echocardiography (see above), ALAT, ASAT, complete blood count, hsCRP, NT-proBNP, creatinine, GFR, sST2, CA 125, and bio-ADM.

9. Primary and secondary Endpoints	
Explorative analyses of:
 
 
• NT-pro-BNP
 
• GFR
 
• The percentage of patients who have elevated pulmonary pressure but are hypo- or euvolemic
 

### 3. BACKGROUND AND SCIENTIFIC RATIONALE

The absolute number of HF-hospitalizations and the rates of HF readmission is still high with a significant financial burden associated. As a result, reducing readmission rates has become a priority in many of the developed countries. Currently 25% of patients with HF are readmitted within one month of discharge and 30% of them within 90 days.

Achieving and maintaining an euvolemic status through managing congestion is a key goal in the management of HF. As a response to the reduced cardiac output, the human body attempts to maintain an effective mean arterial pressure through a series of compensatory mechanisms. Over-activation of the sympathetic nervous system and renin–angiotensin–aldosterone system are among the earliest pathophysiological responses along with an increased metabolic rate driven by an active inflammatory process. Over the course of days to weeks, the body starts to retain salt and water. Paired with a decreased vascular compliance due to vasoconstriction, patients at this stage retain fluid, increase cardiac filling pressures, increase interstitial pulmonary fluid, and lastly increase weight. Severe congestion is supposed to be associated with inflammation, mechanical stress, and endothelial dysfunction.

Thus, close observation of, and rapid response to changes to early patho-physiological indicators are essential in achieving and maintaining euvolemia. However, congestion as a clinical marker of cardiac decompensation, which is defined clinically as peripheral edema (ankle, sacral, scrotal), jugular vein distention, pleural effusion, or ascites, is preceded by an increase in filling pressures and autonomic adaptation. Furthermore, clinical signs and symptoms are neither sensitive nor specific for detecting congestion. Additionally, we have shown in a previous study in patients with HF and sleep apnea increased amounts of both extracellular and total amounts of water compared to those with HF but without sleep apnea. This increased amount of water was not associated with overt clinical cardiac decompensation. We called this clinically pre-congestion. The amount of water was associated with worse exercise capacity and with higher values of apnea/hypopnea index.

As such, new means and technologies to improve monitoring of such parameters and care delivery are urgently needed. Novel technologies of telemedicine or remote monitoring (RM) such as CardioMEMS™ (Abbott Laboratories, Chicago, IL, USA)

represents a good solution to the above-mentioned unmet needs in patients with HF. Pulmonary artery-pressure-guided management of patients with HF proved to reduce morbidity and mortality in this group of patients. However, the principle that volume equals pressure was challenged recently. Based on data from CardioMEMS™ and systems enabling estimation of the intravascular volume such as blood volume analysis (BVA-100, Daxor Corporation, New York, NY, USA), the current approach of HF-therapy using diuretics to decongest these patients appeared not to be always the best clinical decision. The reason is that some of those patients with elevated pulmonary pressure (CardioMEMS™) appeared to be euvolemic or hypovolemic. It was postulated that congestion is a result of changes occurring in both volume and pressure.

Currently, there is no study that evaluated continuously and simultaneously both volume and pressure in patients with HF. This is indeed an important approach and clinically relevant question since this might lead to an adjustment of our practice by characterizing or phenotyping congested patients into elevated/low pressure with hypervolemic, euvolemic or hypovolemic. Managing congestion in patients with HF might be optimally achieved by both monitoring pulmonary pressure and volume status. Additionally, using surrogate biomarkers could be very helpful in better understanding congestion and its management.

## 4. OBJECTIVE AND HYPOTHESIS

### 4.1 OBJECTIVE OF THE STUDY

We plan a mechanistic RM-study in patients with HF with preserved ejection fraction (HFpEF), who have the indication for RM using CardioMEMS™. Data transmitted from CardioMEMS™ and from the smart scale (BWA) will be monitored on daily basis in order to understand the mechanism of changes taking place during the study duration (6 months) in both pulmonary pressure and in volume represented as extracellular and total amount of water in upper and lower extremities as well as in the trunk. This should allow us to reach an euvolemic state in patients with HF, which is often an unmet need. This is especially true in patients with HFpEF.

## 4.2 HYPOTHESIS

Pulmonary artery pressure-guided management of HF patients through CardioMEMS™ is a well-established and evidenced-based method to reduce mortality and hospitalization rate for HF. We hypothesize that expanding RM by using a smart scale (BWA) to measure extracellular and total amount of water in different body compartments would improve the management of congestion in patients with HF. Furthermore, the data of our study will lead to a new paradigm characterizing different phenotypes of patients with HFpEF with different pressure-volume constellations. By adjusting the HF-management accordingly, an improvement of NT-pro-BNP and renal function is expected to occur.

## 5. PRIMARY AND SECONDARY ENDPOINTS

In this pilot mechanistic study, we are focusing on understanding the pressure-volume relationship. Thus, our endpoints will be an explorative analysis of:

- NT-pro-BNP
- GFR
- The percentage of patients who have elevated pulmonary pressure but are hypo- or euvolemic.

NT-pro-BNP will be corrected for BMI by reducing 4% per BMI unit over 25 kg/m^2. This formular was applied similarly in the Guide-HF-trial. 

## 6. DURATION OF THE STUDY AND THE PLANNED TESTS

The planed follow-up duration is 6 months. Time from first patient in to last patient out will be 12 months.

**All patients will get following tests at baseline:** Echocardiography (left ventricle ejection fraction (LVEF), E/e', left atrial volume index (LAVI), left atrial strain analysis, left ventricle mass index (LVMI), tricuspid annular plane systolic excursion (TAPSE), right ventricle strain, inferior vena cava IVC), and blood tests: N-terminal pro-b-type natriuretic peptide (NT-proBNP), creatinine, glomerular filtrating rate (GFR), soluble suppression of tumorigenicity (sST2) as a surrogate of intravascular congestion,

carbohydrate antigen 125 (CA 125) and bio-adrenomedullin (bio-ADM) as surrogates of tissue congestion (extracellular water). Additionally, ALAT, ASAT, complete blood count, and hsCRP will be documented. Evaluation of extracellular and total amounts of water volume segmentally (arms, legs, trunk) using the smart scale (BWA) as well as pulmonary pressure (CardioMEMSTM) will be done daily at the same time.

Following blood tests will be monitored **at days 14, 42, 90** and at the final visit: NT-proBNP, creatinine and GFR, hemoglobin, hematocrit, hsCRP, sST2, CA 125, and bio-ADM.

Blood draw will be 20 ml Blood (Serum and EDTA) in each visit.

**Tests and investigations at the final visit:** Echocardiography (see above), ALAT, ASAT, complete blood count, hsCRP, NT-proBNP, creatinine, GFR, sST2, CA 125, and bio-ADM.

**Bioelectrical-Impedance Analysis (BIA):** It is a non-invasive measurement of the body composition, i.e. muscle, fat, water. Measurements will be performed in standing positions using (Body water scale InBody, South Korea), which is capable to measure body amounts of water in different compartment non-invasively, reliably, and objectively based on bioelectric impedance (BIA)-technology. Patients who have implanted cardiac devices will be excluded.

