## **8. PROJECT TIMELINE & FUTURE PLANS**

We will be able to begin our study in April 2024. We have previous experience with an established HF population. We expect to reach full recruitment by the end of 2024. Data will be analyzed immediately with focus on presenting initial results in the annual meeting of the European society of Cardiology 2025. We expect to have a full analysis for manuscript preparations by June 2025.

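### Does the 12-month span from first patient in to last patient out clash with recruitment to the end of 2024 and a full analysis by June 2025?

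*Protocol*

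**What the plan says.** The Protocol gives the overall duration twice. Section 6 says "Time from first patient in to last patient out will be 12 months", and item 7 of the synopsis (section 2) says "Time from first patient in to last patient out 12 months". Follow-up per patient is also in section 6: "The planed follow-up duration is 6 months". Table 1 in section 7.2 places the final visit at Day 180 and applies the schedule to all participants.

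The calendar is in section 8. On the start it says "We will be able to begin our study in April 2024", on enrolment "We expect to reach full recruitment by the end of 2024", and on reporting "We expect to have a full analysis for manuscript preparations by June 2025". Section 15 repeats the June 2025 expectation.

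Section 11 sets the target at 20 patients, raised to 25 for an expected 20% drop-out. Section 12 says that missing data will be handled by multiple imputation.

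**The concern.** Twelve months in total, less 6 months of follow-up for the last patient, leaves 6 months to enrol. April to the end of December is 8 to 9 months. On the plain reading of section 8, sections 2 and 6 are therefore 2 to 3 months short, and the last Day 180 visit comes at the very end of the month by which the full analysis is expected.

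This would matter if someone enforced the shorter timetable. Day 180 carries the only follow-up echocardiogram and the final NT-proBNP and GFR. If the study were closed 12 months after the first patient, or the database cut at the start of June 2025, late-enrolled patients would have no Day 180 data. Multiple imputation would then be filling a gap made by the calendar. The target leaves no slack, since 25 × 0.8 = 20.

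**Working it through.** **Inputs.** Span 12 months (sections 2 and 6). Follow-up 6 months, final visit Day 180 (section 6; Table 1). Start in April 2024, day not given, so taken as 1 to 30 April. Recruitment complete by 31 December 2024 at the latest, and full analysis by June 2025 (section 8). One month is taken as 30.4375 days.

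**Can the 12 months be reproduced?** Span = (last patient in + 180 days) − first patient in.

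With the last patient in on 31 December 2024, the last patient out is 31 December 2024 + 180 days = 29 June 2025 (30 June if counted as six calendar months). Then:

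| First patient in | Days to 29 June 2025 | Months |
|---|---|---|
| 1 April 2024 | 454 | 14.9 |
| 15 April 2024 | 440 | 14.5 |
| 30 April 2024 | 425 | 14.0 |

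So 12 months is not reproduced if the first patient enters in April and recruitment runs to the last day of the year.

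**Which dates do give 12 months?**

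- First patient in on 1 April 2024: the span ends on 1 April 2025, and 180 days earlier is 3 October 2024.
- First patient in on 30 April 2024: the span ends on 30 April 2025, and 180 days earlier is 1 November 2024.
- Last patient in on 31 December 2024: 29 June 2025 − 365 days = 29 June 2024 as the earliest first patient in.

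The first two are consistent with every date in section 8, because recruitment finished in October is finished by the end of the year. They put the last visit in April 2025, at least one month before the start of June. The third is also possible, because being able to begin in April is not the same as enrolling a patient in April.

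**The June 2025 analysis.** In the latest case the last visit is on 29 or 30 June 2025, still within June. Follow-up does not run past the month, but it leaves practically no time for cleaning and analysis. A last visit by 31 May 2025 needs the last patient in by 31 May 2025 − 180 days = 2 December 2024.

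**What an enforced 12-month close would cost.** This assumes even enrolment up to 31 December 2024 and a hard close.

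- Start 1 April: 89/274 = 32.5% enrol after 3 October; 0.325 × 25 = 8.1 patients without Day 180. After drop-out, (25 − 8.1) × 0.8 = 13.5 reach it.
- Start 30 April: 60/245 = 24.5% enrol after 1 November; 0.245 × 25 = 6.1 patients. After drop-out, (25 − 6.1) × 0.8 = 15.1 reach it.

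These losses need a closing rule, and the Protocol has none. Sections 6 and 7.2 give each participant 6 months of follow-up with a Day 180 visit. Followed as written, late recruitment delays the end of the study and costs no Day 180 visits.

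**The case for a change.** The best case for a change is that this is something the Protocol states, not something left for a later document. The 12 months appear twice and June 2025 twice. No first enrolment in April combined with recruitment to year-end gives 12 months, and the combinations that do fit use an enrolment close or a first-patient date that the Protocol never gives. It also does not say that the final analysis waits for every patient's Day 180 visit or withdrawal, and correcting the dates would cost only a text edit.

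Part of this stands. The sections do not agree on the plain reading, and anyone relying on the timetable should read the span as possibly 14 to 15 months, with June 2025 as optimistic.

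The rest does not carry the point further. The section 8 dates are worded as readiness and expectation, and an end-of-year limit is a latest date. The loss of 6 to 8 patients follows only from enforcing a limit that nothing in the Protocol enforces, and it also assumes even enrolment. Nor does section 11 define its 20 patients by having Day 180 data, and section 5 ties no endpoint to that visit. The main aim, the pressure-volume relationship, rests on daily measurements. Even at a hard close on 1 April 2025, a patient enrolled on 31 December 2024 would have passed Day 90 (31 March 2025). When to lock the data is a detail commonly left to the statistical analysis plan.

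**Conclusion.** No change to the plan follows. The inconsistency is a clerical one between planning forecasts: 12 months against 14.0 to 14.9 months if the first patient enters in April 2024 and the last on 31 December 2024. It disappears if enrolment closes between 3 October and 1 November 2024, or if the first patient enters no earlier than about 29 June 2024.

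No endpoint, sample size or analysis uses the 12-month figure. Each patient's follow-up is set by time since entry, so a slower calendar moves the report by 2 to 3 months and leaves the results as they are. This rests on every participant being followed to Day 180, as sections 6 and 7.2 provide. It would fail only if the study were closed, or the data cut, on a calendar date before those visits were complete, and the Protocol sets no such date.

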## 7. RESEARCH DESIGN & METHODOLOGY

### 7.1 STUDY DESIGN

MAGIC-HF is a streamlined, prospective, mechanistic, non-randomized, study. This study will investigate the value of adding volume-based RM to the well-established pulmonary artery pressure monitoring in patients with HFpEF in understanding the volume-pressure relationship. The study will take place in the department of cardiology, University Hospital Magdeburg.

### 7.2 STUDY POPULATION

**Inclusion criteria:**

- 1) 18 years of age or older.
- 2) Patients with HFpEF hospitalized for acute decompensated heart failure and require treatment with intravenous (IV) diuretics.
- 3) signed informed consent.

**Exclusion criteria:**

- 1) Patients admitted with cardiogenic shock and/or those who required inotropic or vasopressor support.
- 2) had a history of cardiac transplantation or ventricular assist device (VAD) implantation.
- 3) had any implanted cardiac device (pacemaker, ICD, CRT-D).
- 4) had chronic kidney disease with creatinine clearance < 20 ml/min.
- 5) had recent acute MI or CABG within 3 months.

**Timetable of the study:** All participants will undergo a standardized series of assessments as shown in table 1.

Table 1: Timetable of the study

	Day 0	daily	Day 14	Day 42	Day 90	Day 180
Informed consent	x					
Echocardiography	x					x
Body composition-Water assessment	x	x	x	x	x	x
CardioMEMS™-Measurement	x	x	x	x	x	x
Blood tests	x		x	x	x	x

## **8. PROJECT TIMELINE & FUTURE PLANS**

We will be able to begin our study in April 2024. We have previous experience with an established HF population. We expect to reach full recruitment by the end of 2024. Data will be analyzed immediately with focus on presenting initial results in the annual meeting of the European society of Cardiology 2025. We expect to have a full analysis for manuscript preparations by June 2025.

## **10. INFORMATION & INFORMED CONSENT**

Subjects will sign an informed consent before any investigation of the designed study will be conducted.

## **11. SAMPLE SIZE AND STATISTICS**

There is not enough prior data to calculate the sample size. Our aim primarily is to describe the relationship between pressure-volume as part of the management of HF-management. We suppose that in this pilot study 20 patients should be sufficient to understand this relationship and the mechanism beyond it. With expected 20% drop-out rate, we intend to recruit 25 patients.

All data and statistics will be reported as mean  $\pm$  standard deviation ( $n \pm SD$ ) for continuous normally distributed data or as median and interquartile range [25–75%] for variables that were not normally distributed, respectively. Categorical data will be summarized by percentages. Kaplan-Meier analyses with a log-rank test will be used for presenting time-to-event data. Daily measurements of CardioMEMS™ and BWA will

be depicted over the study time. A comparison between events represented by increased pulmonary pressure and increased volume higher than the defined cut-off for each patient respectively will be performed. The Statistical Package for Social Sciences software (SPSS 28, IBM, Armonk, USA) will be used for statistical analysis. The chi-squared test will be used to look for trend for categorical variables and Kruskal Wallis test will be applied for not normally distributed data, respectively. Analysis of variance (ANOVA), Pearson's or Spearman simple regression will be used as appropriate. A two-tailed p-value  $<0.05$  indicates statistical significance.

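### Section 11 assigns the Kruskal-Wallis test to all non-normal data, but the expected improvement in NT-proBNP and renal function is a change across five visits in the same patients

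*Protocol*

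**What the plan says.** Section 11 chooses tests by type of data, not by endpoint or contrast. For non-normal data the rule is unqualified: "Kruskal Wallis test will be applied for not normally distributed data". Chi-squared is named for categorical variables. For the rest, "Analysis of variance (ANOVA), Pearson's or Spearman simple regression will be used as appropriate". Significance is two-tailed at 0.05. The SAP summary in section 12 adds intention-to-treat, Kaplan-Meier curves with a log-rank test between groups, and multiple imputation. Neither section names a paired or repeated-measures method.

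The expected effect appears in the Synopsis ("This leads as a result to an improvement of NT-pro-BNP and renal function") and in section 4.2 ("an improvement of NT-pro-BNP and renal function is expected to occur"). NT-proBNP and GFR are two of the three exploratory endpoints in section 5.

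On design, section 7.1 says "MAGIC-HF is a streamlined, prospective, mechanistic, non-randomized, study" and describes no comparator. Section 7.2 says "All participants will undergo a standardized series of assessments as shown in table 1", and Table 1 there puts blood tests at days 0, 14, 42, 90 and 180.

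**The concern.** With one cohort on one schedule, improvement can only be shown by comparing each patient's later values with the same patient's earlier ones. Those values are correlated. Kruskal-Wallis treats the visits as separate groups of different people, so it ignores the pairing, which is where most of the information lies when patients differ a lot from one another.

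This is more than silence on a detail. The protocol names a test for non-normal data, and for this comparison it is the wrong one. NT-proBNP is commonly skewed, so the rule may well apply to it. What is at stake is a real, moderate improvement being reported as non-significant because of the test, in a study of only 20 evaluable patients.

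**Working it through.** **The plan's own figure.** 20 evaluable patients with 20% dropout gives 20 / (1 − 0.20) = 25, as stated. Section 11 says prior data are too few for a sample size calculation, so there is no power figure to reproduce.

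**Inputs from the protocol.** n = 20 evaluable; five blood-test visits (Table 1); two-sided alpha 0.05.

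**Assumptions, not in the documents.** Normal values (for NT-proBNP, on the log scale) with equal SD at each visit; equal within-patient correlation ρ of 0.1, 0.5 or 0.7; a fall of 0.44 SD reached in steps of 0, 0.5, 0.75, 1 and 1 times the full fall. Rank tests give the same p-values on raw log-normal values as on their logs. In percent, the fall is 1 − exp(−0.44 × log SD): 27% for a log SD of 0.7 and 38% for 1.1.

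**Why the direction is certain.** Take day 0 against day 180, in SD units.

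- Standard error of the mean change as independent groups: √(2/20) = 0.316, whatever ρ is.
- True standard error in the same patients: √(2(1 − ρ)/20) = 0.300 at ρ = 0.1, 0.224 at 0.5 and 0.173 at 0.7.
- A fall of 0.44 SD is therefore 0.44/0.316 = 1.39 standard errors when pairing is ignored. With pairing it is 1.47, 1.97 and 2.54 standard errors.

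These ratios are for means, but the rank tests follow the same logic. Ignoring a positive correlation overstates the error, so the test rejects too rarely.

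**Simulation (n = 20).**

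| ρ | Type I error, Kruskal-Wallis, 5 visits | Power, Kruskal-Wallis v Friedman, 5 visits | Power, day 0 v day 180, Kruskal-Wallis v Wilcoxon signed-rank |
|---|---|---|---|
| 0.1 | 3.4% | 18% v 19% | 24% v 27% |
| 0.5 | about 0.2% | 7% v 33% | 20% v 45% |
| 0.7 | 0.0% | 3% v 50% | 16% v 66% |

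Friedman's type I error stays at 4.5-5.1%. Repeat runs moved the power figures by about two points at most. A separate run with a linear fall of 0.5 SD agreed in direction: 9% against 37% at ρ = 0.5 and 4.5% against 56% at 0.7.

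**Where the choice matters less.** At ρ = 0.1 and a fall of 0.78 SD, Kruskal-Wallis has 56% power and Friedman 53%. At a fall of 1.11 SD, Kruskal-Wallis reaches 90-95%. In between, at 0.78 SD and ρ of 0.5 to 0.7, it has 44-49% against 82-97% for Friedman.

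**The case against.** The strongest reply is that section 11 is a general list of tools and never says that Kruskal-Wallis will be run across visits. A proper use is in view: section 3 speaks of "phenotyping congested patients into elevated/low pressure with hypervolemic, euvolemic or hypovolemic", and for several independent groups of that kind Kruskal-Wallis, chi-squared and one-way ANOVA are suitable. Section 12 also foresees comparisons between groups. A fuller SAP may exist, and a longitudinal model is commonly left to it. All of this lowers the weight. It does not remove the point, because the sentence on non-normal data is unqualified, is not tied to phenotypes, and as written covers the comparison that the hypothesis calls for.

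Three stronger readings are tempting, and the documents do not support them.

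- A reader might infer that no listed method can handle repeated visits. ANOVA is to be used as appropriate, which leaves room for a repeated-measures form for roughly normal data, including GFR or log-transformed NT-proBNP. The gap is for endpoints handled as non-normal.
- A reader might infer that simple correlation will be run on pooled patient-days and so produce false positives. Section 4.1 says "Data transmitted from CardioMEMS™ and from the smart scale (BWA) will be monitored on daily basis" and section 11 says the daily readings will be plotted, but nothing assigns Pearson or Spearman to pooled days. The comparison of pressure and volume events names no test. No error can be claimed for either.
- A reader might take the power figures as properties of this trial. They rest on assumed correlations and effects.

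The percentage endpoint in section 5 is one value per patient and is not affected.

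**Conclusion.** The point holds in a limited form. As written, the rule for non-normal data applies an independent-samples test to paired data when NT-proBNP or GFR is compared across visits. The error is conservative: it risks a missed improvement, not a false claim. The direction follows from any positive within-patient correlation. The loss is large when that correlation is about 0.5 or more and the change is moderate, and negligible when the correlation is near 0.1. Because the documents give neither an SD nor a correlation, no loss of power can be attributed to the plan itself. The study is a pilot with exploratory endpoints and no confirmatory decision depends on the test, so the severity is minor.

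**What to change.** In section 11:

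- State that change in log NT-proBNP and in GFR over days 0, 14, 42, 90 and 180 is analysed with a repeated-measures mixed model (or repeated-measures ANOVA). If the data are handled as non-normal, use Friedman over the five visits and Wilcoxon signed-rank for baseline against day 180.
- Restrict Kruskal-Wallis, chi-squared and one-way ANOVA to comparisons between independent groups with one value per patient, such as pressure-volume phenotypes or baseline values.

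The cost is a few sentences and slightly more analysis work. No new data, visits or patients are needed.
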